10.2 Measurement of Treatment Compliance

Study drug dosing compliance (in percentage) during the open-label study period for a subject is defined as:

$$\frac{(\text{total number of tablets actually taken})}{(\text{total number of tablets expected to be taken})} \times 100.$$

The total number of tablets actually taken is calculated as:

$$(\text{the total number of tablets dispensed}) - (\text{the total number of tablets returned}).$$

The total number of tablets expected to be taken is calculated as:

$$(\text{the duration of exposure}) \times 2.$$

For any visit with unreturned drug kits, the total number of tablets actually taken will be imputed as the total number of tablets expected to be taken for that visit period.

Compliance will be summarized as both continuous and categorical variables. For categorical presentation, the number and percentage of subjects in each of the following categories will be presented: <80%, 80 to 120%, and >120%.

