#### **5.1.1 Formulation, Appearance, Packaging, and Labeling**

The Sponsor will supply pimavanserin 17 mg tablets.

Pimavanserin tartrate is a white to off-white powder. Pimavanserin 17 mg tablets include the active compound (pimavanserin tartrate) and the following excipients: pregelatinized starch, magnesium stearate, and microcrystalline cellulose, and the tablet coating is [REDACTED]. The drug product is formulated with standard pharmaceutical excipients at 17 mg strength (20 mg of pimavanserin tartrate).

Pimavanserin tablets are manufactured under current Good Manufacturing Practices.

During the treatment period, study drug will be distributed in a quantity sufficient to ensure the subject has an adequate supply of study drug between study visits. In addition to the study drug dispensed at the site, investigational product may be delivered to the subject's home.

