### **5.1.6 Study Drug Compliance**

If a subject misses one dose of study drug, he or she should not take an extra dose the next day. Subjects who are less than 80% compliant with study drug as assessed at more than one study visit should be discussed with the Medical Monitor or designee.

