5.4 Data Handling Conventions

5.4.1 Missing or Incomplete Date for Last Dose of Study Drug

In the Safety Analysis Set, if the last dose date of study drug is missing for a subject who completed or early terminated from the study, then the missing last dose date of study drug will be imputed using the last expected dosing date or EOT/ET date, whichever occurs earlier. The last expected dosing date will be calculated as the last drug dispense date plus the expected dosing interval days. For the incomplete last dose date of the study drug, the imputation algorithms will be detailed in the analysis dataset specification document. The missing or incomplete dates will be displayed in the data listings as reported on the eCRF rather than the imputed dates.

For the data summarization before final database lock, if a subject is still ongoing, then this subject's last dose date will be imputed using the database extract date.

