10.1 Exposure to Study Drug

10.1.1 Exposure to Open-label Pimavanserin

For each subject, the duration of exposure to open-label pimavanserin (open-label last dose date – open-label first dose date + 1) will be calculated and summarized. The number and percentage of subjects within each of the following exposure levels in terms of duration of exposure will also be tabulated: <2 week (1 to 13 days), 2 to <4 weeks (14 to 27 days), 4 to <8 weeks (28 to 55 days), 8 to <12 weeks (56 to 83 days), 12 to <16 weeks (84 to 111 days), 16 to <28 weeks (112 to 195 days), 28 to <40 weeks (196 to 279 days), 40 to <52 weeks (280 to 363 days), ≥52 weeks (≥364 days).

In addition, the maximum dose in the open-label period, final dose in open-label period, and the mean daily dose during open-label period will be determined for each subject and summarized. The mean daily dose will be calculated as the number of pimavanserin tablets taken in the open label period multiplied by 17 (mg) divided by the duration of total exposure in the open-label period in days.

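### SAP 10.2 counts every visit period with unreturned kits as full intake, with no sensitivity summary and no count of imputed periods, so some measured non-compliers can leave the below-80% category

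*SAP*

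**What the plan says.** SAP 10.2 defines open-label compliance as tablets taken divided by tablets expected, times 100. Tablets taken are dispensed minus returned. Tablets expected are days of exposure times 2. One exception follows: "For any visit with unreturned drug kits, the total number of tablets actually taken will be imputed as the total number of tablets expected" for that visit period. Results are shown as a continuous variable and in three categories: below 80%, 80 to 120%, and above 120%.

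Three other provisions bear on how the rule works.

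- SAP 10.1.1 defines exposure as "open-label last dose date – open-label first dose date + 1", so the denominator ends at the last dose.
- SAP 5.4.1 says that a missing last dose date is "imputed using the last expected dosing date or EOT/ET date, whichever occurs earlier". The last expected dosing date is the last dispensing date plus the dosing interval.
- SAP 10.1.1 and 10.1.2 compute mean daily dose from the number of tablets taken times 17 mg over the days of exposure. Neither says whether imputed tablets are included.

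SAP 10.2 plans no alternative calculation and no tabulation of how many subjects or periods were imputed.

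**The concern.** The rule fills missing accountability data with the best case. By contrast, SAP 5.4.4 and 5.4.5 fill missing adverse event severity and causality with the worst case. Because the trigger is any unreturned kit at a visit, a partial return for the same period also appears to be discarded.

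Unreturned kits are foreseeable here. Protocol 3.1.3 allows telephone and video visits, Protocol 5.1.1 says "In addition to the study drug dispensed at the site, investigational product may be delivered to the subject's home", and SAP 3.6 records that the study was stopped early and the remaining subjects were discontinued. SAP 3.1 has drug dispensed at Baseline and Weeks 4, 8, 12, 16, 28 and 40, so from Week 16 one imputed period can cover 84 days.

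The compliance and dose summaries tell the reader how much drug lies behind the adverse event rates in a study whose primary objective is long-term safety. The 80% cut also matters to the protocol, whose section 5.1.6 says: "Subjects who are less than 80% compliant with study drug as assessed at more than one study visit should be discussed with the Medical Monitor".

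**Working it through.** The plan gives no compliance figure or return rate to reproduce, so the SAP 10.2 formula is applied to constructed subjects. The adherence values are assumptions. The expected count for a period is taken to stop at the last dose, as the definition from exposure days implies.

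**Inputs**
- Two tablets a day; intervals from the dispensing weeks in SAP 3.1.
- Weeks 0–16: 112 days × 2 = 224 tablets expected.
- Weeks 0–40: 280 × 2 = 560.
- One 84-day interval: 84 × 2 = 168.

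**1. Measured 70% through Week 16, full Week 16–28 interval unreturned.** Tablets counted: 0.70 × 224 ≈ 157. Reported: (157 + 168)/(224 + 168) = 325/392 = 82.9%, so the subject leaves the below-80% category. If true intake in the unreturned interval were 30% to 90%, true compliance would be 52.9% to 78.6%. On returned kits only, the figure is 70%.

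**2. Same subject, last dose 28 days into that interval.** Imputed: 28 × 2 = 56. Reported: (157 + 56)/280 = 76.1%, still below 80%.

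**3. Measured 70% through Week 40, only the last interval unreturned.** (392 + 168)/728 = 76.9%, still below 80%.

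**4. Measured compliance c needed to reach a reported 80%**
- One full 84-day interval after Week 16: (224c + 168)/392 ≥ 0.80 gives c ≥ 0.65.
- Two such intervals: (224c + 336)/560 ≥ 0.80 gives c ≥ 0.50.
- Only the last interval, after Week 40: (560c + 168)/728 ≥ 0.80 gives c ≥ 0.74.

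**5. What dispensed minus returned gives without the rule**
- Only supply is 28 days (56 tablets), last dose on Day 14, nothing returned: 56/28 = 200%. The rule gives 28/28 = 100%.
- Case 2: (157 + 168)/280 = 116%. The rule gives 76.1%.

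**6. Last dose date missing.** Suppose 90% through Week 16 (201.6 tablets), full intake for 10 days after the Week 16 dispensing (20 tablets), then stopping, with no last dose date and no earlier EOT/ET date. SAP 5.4.1 sets exposure at 112 + 84 = 196 days and SAP 10.2 credits 168 tablets for the interval. Reported: (201.6 + 168)/392 = 94.3%. Tablets really taken over the same denominator: 221.6/392 = 56.5%. Over the true 122 days, compliance was 221.6/244 = 90.8%. The combined error therefore lies mostly in 74 days of exposure that did not occur, each credited with full dosing.

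**7. Mean daily dose, if imputed tablets enter it.** Case 1: 325 × 17/196 = 28.2 mg, against 157 × 17/112 = 23.8 mg on returned kits.

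**8. Possible size across the study.** If a share f of subjects is wholly imputed and their true adherence is a, mean compliance is overstated by f × (1 − a). This gives 0.5 points at f = 5%, a = 90%, and 21 points at f = 30%, a = 30%. Both inputs are assumed; the documents give neither.

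**The case against.** A reader might infer that anyone who stops or drops out without returning drug is reported as a perfect taker. The documents do not support that. When the last dose date is known, days after it enter neither numerator nor denominator. Undosed days are credited only when the date is missing and SAP 5.4.1 fills it in. Full compliance describes the imputed period; a subject reads 100% only if every period is imputed or the measured ones already average 100%.

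A reader might also infer that the rule always raises compliance. Against true intake at or below the expected count it can only raise the figure or leave it unchanged. Against the SAP's own dispensed-minus-returned count it lowers the figure for early stoppers (step 5), so it serves a purpose.

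Nor do the documents show that unreturned kits come mainly from dropouts. They give no return pattern, and some provisions work the other way: drug may be returned to staff on home visits (Protocol 5.2), remote visits ask about study drug compliance (Protocol 6.3.8.1), and reasonable efforts are made to complete the ET visit (Protocol 4.4.1).

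The consequences are limited. Compliance defines no analysis set, enters no test and is not used in the adverse event tables. Nothing links the SAP imputation to the Medical Monitor discussions in Protocol 5.1.6. All collected data will be listed (SAP 5), and table specifications sit in a separate document (SAP 1), so the missing count is a reporting gap in the SAP.

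All of this stands and narrows the point. It does not remove it: the only planned compliance figure assumes full intake where intake is unknown, and a reader of the summary could not tell how much of it was measured.

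**Conclusion.** The point holds as a narrow, inexpensive improvement. SAP 10.2 overstates intake in any imputed period in which doses were missed. It can move a subject from below 80% to 80 to 120%, as in the 82.9% example, but need not, as the 76.1% and 76.9% examples show. The 65% and 50% thresholds apply only to full 84-day intervals directly after Week 16. A missing last dose date can compound the overstatement.

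The effect is confined to the descriptive compliance summary and, depending on an unstated choice, mean daily dose. Its size cannot be determined without a return rate; the 0.5 to 21 point range rests wholly on assumed inputs. That one unreturned kit overrides the whole period's count is the natural reading of the wording, but the SAP does not spell it out.

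**What to change.** - In SAP 10.2, keep the imputed figure and show beside it compliance computed only over intervals with returned kits, dropping unreturned intervals from both numerator and denominator. Add a not-evaluable row for subjects with no accountable interval.
- Report the number and percentage of subjects and of intervals imputed.
- In SAP 10.1.1 and 10.1.2, state whether imputed tablets enter mean daily dose, and give mean daily dose on the same returned-kit basis.
- Do not delete the rule without a replacement, because the raw count would return the inflated values in step 5.

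The cost is a few lines of SAP text and a small programming change, using data already collected. Some subjects become not evaluable, and these may include dropouts. The restricted summary says nothing about intake in the dropped intervals and represents the whole period only if adherence there was similar, which is why both figures should be shown. Reported compliance may look slightly less favourable.

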11 CONCOMITANT AND POST-TREATMENT MEDICATION

Concomitant medication is defined as any medication with a start date prior to the date of the open-label first dose and continuing after the open-label first dose date or with a start date between the open-label first dose date and open-label last dose date, inclusive. Any medication with a start date after the open-label last dose date will be considered as post-treatment medication. Concomitant and post-treatment medications will be summarized separately. Relationship to COVID-19 will be assessed for selected medications as detailed in the GSD. Concomitant and post-treatment medication analyses described above will also be

summarized by relationship to COVID-19 (Not related to COVID-19 vs. Related to COVID-19).

Medications will be coded using WHO Drug Dictionary March 2020. For concomitant medications, the number and percentage of subjects taking each drug class (ATC Level 3) and medication preferred term will be tabulated for Safety Analysis Set. A subject will be counted only once per drug class or per medication preferred term for the summary.

12 EFFICACY ANALYSES

All efficacy analyses will be performed for the Safety Analysis Set. No hypothesis testing is planned. Descriptive summaries of all efficacy endpoints will be provided.

12.1 Efficacy Variables

Efficacy Endpoints

- Change from Baseline in Hamilton Depression Scale (17 items) (HAM-D-17) total score
- Treatment responder rates. Treatment response is defined as a reduction from Baseline in HAM-D-17 total score of 50% or more.
- Treatment remission rates. Treatment remission is defined as a HAM-D-17 total score ≤ 7 .
- Change from Baseline in Clinical Global Impression–Severity (CGI-S) score for depressive symptoms
- Change from Baseline in Sheehan Disability Scale (SDS) mean score
- Change from Baseline in the Changes in Sexual Functioning Questionnaire Short Form (CSFQ-14) total score
- Change from Baseline in Karolinska Sleepiness Scale (KSS) score

12.2 Adjustment for Covariates

Not applicable.

12.3 Handling of Missing Data

Any derived scores (i.e. total, domain, or subscale scores) that are missing, after the imputation of individual missing items as described in [Section 5.2](#), will not be imputed.

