### **4.4 Subject or Study Discontinuation**

Subjects may be discontinued from the study for a number of reasons, including, but not limited to, those listed below:

- Adverse event
- Death
- Lack of efficacy
- Lost to follow-up (Section 4.5)
- Non-compliance with study drug
- Physician decision
- Pregnancy
- Protocol deviation
- Study terminated by Sponsor
- Use of prohibited medication
- Other

The Sponsor reserves the right to discontinue the study at any time for any reason. Such reasons may be any of, but not limited to, the following:

- Occurrence of AEs unknown to date in respect of their nature, severity, and duration or the unexpected incidence of known AEs
- Medical, ethical or business reasons affecting the continued performance of the study

Regulatory authorities also have the right to terminate the conduct of the study in their region for any reason.

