### **9.2 Statistical Hypotheses**

No formal testing of hypotheses is planned. All outcomes will be summarized descriptively.

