3.5 Determination of Sample Size

It is estimated that approximately 420 subjects from Study ACP-103-054 and Study ACP-103-059 will be eligible to enter this study. The sample size for this study is not based on statistical power, but will depend on the number of subjects who transition into this open-label extension study from the antecedent studies, Study ACP-103-054 and Study ACP-103-059.

ACP-103-054, -059 and -055 were stopped early; the estimated number of subjects will be less than originally estimated.

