5.1 General Data Reporting Conventions

For continuous variables, the following summary statistics will be provided: number of subjects, mean, standard error of the mean (SE), standard deviation (SD), minimum, maximum, and median. Unless specified otherwise, means, and medians will be presented to one more decimal place than the raw data, and the SDs and SEs will be presented to 2 more decimal places than the raw data.

For categorical variables, summaries will include the number and percentage of subjects in each category, using the number of subjects with non-missing values as the denominator for the percentages (unless otherwise specified). Categories with zero counts will not have zero percentages displayed. Percentages will be presented to 1 decimal place.

When converting number of days to months, it will be calculated as the number of days divided by 365.25 and then multiplied by 12. When converting number of days to years, it will be calculated as the number of days divided by 365.25.

No hypothesis testing is planned. Descriptive summaries of all safety and efficacy endpoints will be provided.

All safety and efficacy endpoints will be summarized for the Safety Analysis Set. In addition, summaries by treatment group according to the original double-blinded treatment actually received in the antecedent study (placebo or pimavanserin) will also be provided.

For each continuous measure in safety and efficacy analyses, change from Baseline results will be presented in two ways:

1. Main analysis: using the Baseline from Study ACP-103-055 and reporting the changes across Study ACP-103-055 timepoints
2. Exploratory analysis: using the Baseline from the antecedent study (ACP-103-054 or ACP-103-059), and reporting the changes across Study ACP-103-055 timepoints

For the treatment responder rate, the summary will also be presented in two ways:

1. Main analysis: using the Baseline from Study ACP-103-055 and reporting the rate across Study ACP-103-055 timepoints
2. Exploratory analysis: using the Baseline from the antecedent study (ACP-103-054 or ACP-103-059), and reporting the rate across Study ACP-103-055 timepoints

The treatment remission rate and the percentage of subjects with sexual dysfunction will also be summarized across Study ACP-103-055 timepoints using the Baseline from Study ACP-103-055 and the Baseline from the antecedent double-blind studies as reference points.

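### By-visit response and remission rates count only subjects still observed, so selective dropout can raise the later rates with no true improvement

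*SAP*

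**What the plan says.** The endpoints are in SAP 12.1: "Treatment response is defined as a reduction from Baseline in HAM-D-17 total score of 50% or more", and "Treatment remission is defined as a HAM-D-17 total score" of 7 or less. Three provisions together fix how the rates are formed:

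- SAP 5.1 computes categorical summaries "using the number of subjects with non-missing values as the denominator for the percentages", unless another rule is given.
- SAP 12.3 leaves unimputed "Any derived scores (i.e. total, domain, or subscale scores) that are missing, after the imputation of individual missing items".
- SAP 13 tabulates both rates at scheduled timepoints by antecedent double-blind treatment and gives no other denominator.

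SAP 5.3 and 5.3.1 place early-termination and remote assessments in the analysis window where they fall. The main and exploratory versions of the response rate in SAP 5.1 differ only in which Baseline is used. For other rates the SAP does override the default: 14.6.1 (suicidality) and 14.6.3 (sexual dysfunction) use the whole Safety Analysis Set.

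Protocol 4.4 lists "Lack of efficacy", adverse event and termination by the sponsor as separate discontinuation reasons, and SAP 6 tabulates discontinuations by reason. SAP 3.5 and 3.6 record that the study was stopped early and the remaining subjects discontinued.

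**The concern.** This is an observed-case rate. Take a subject who leaves for lack of efficacy with an early-termination visit on study day 75. The score falls in the OL Week 12 window (days 71 to 98) and can count there. From OL Week 16 (day 99 onward) the subject is in neither numerator nor denominator.

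If such exits accumulate, the later rates describe a group increasingly selected for doing well. Exploring long-term benefit is a stated objective, and there is no concurrent control arm in which the same selection would show. A reader who sees remission climb towards Week 52 could not tell improvement from attrition using the rates alone.

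**Working it through.** **Inputs from the documents.** The definitions, denominator and non-imputation rule are as above. For the number of subjects, SAP 3.5 says "It is estimated that approximately 420 subjects from Study ACP-103-054 and Study ACP-103-059 will be eligible to enter this study" and "The sample size for this study is not based on statistical power". The plan states no power, response rate, remission rate or dropout rate, so it has no figure of its own to reproduce. Everything below is illustration.

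**Assumed inputs.** p = true rate among all treated subjects, constant over time; d = fraction lost before the visit; q = rate among those lost.

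**Formula.** Observed-case rate = (p − d·q) / (1 − d).

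**Step 1: vary who leaves** (p = 40%, d = 30%).

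| q among leavers | Calculation | Observed-case rate |
|---|---|---|
| 0% | 0.40/0.70 | 57.1% |
| 10% | 0.37/0.70 | 52.9% |
| 20% | 0.34/0.70 | 48.6% |
| 40% (uninformative) | 0.28/0.70 | 40.0% |
| 60% | 0.22/0.70 | 31.4% |

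The rate rises only if q < p, is unbiased if q = p, and falls if q > p.

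**Step 2: vary how many leave, in the extreme case q = 0.** For d = 10%, 20%, 30% and 40%, p/(1 − d) is 44.4%, 50.0%, 57.1% and 66.7% when p = 40%. It is 22.2%, 25.0%, 28.6% and 33.3% when p = 20%, a lower value that might suit remission. For each d these are upper bounds.

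**Step 3: mixed loss.** Suppose half of the 30% are non-responders and the other half leave at random from the remaining 85%. The rate among that 85% is 0.40/0.85 = 47.1%, and random loss leaves it there.

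**Step 4: test possible repairs on the mixed case.** Let the random half be the sponsor stop. With 420 subjects there are 168 responders. Lack of efficacy removes 63 non-responders, leaving 357; the stop removes 63 more, leaving 294. Observed responders are 168 × 294/357 = 138.4.

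- All missing counted as failures: 138.4/420 = 32.9%, too low because the stop is treated as failure. If the whole 30% loss were uninformative, this approach would give 0.40 × 0.70 = 28.0%.
- Removing only the sponsor-stopped subjects: 138.4/357 = 38.8%, still below 40%. Earlier failures stay in the denominator at visits that some of them could not have reached either.
- Applying the stop date to everyone alike: if the stop is unrelated to outcome, the same fraction 294/357 = 0.824 of all 420 have a planned visit before it, which is 345.9 subjects. Then 138.4/345.9 = 40.0%, the true rate.

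**The case against.** The best defence is that the plan claims little for these rates. The primary endpoint is treatment-emergent adverse events, response and remission are exploratory, and Protocol 9.2 says "No formal testing of hypotheses is planned. All outcomes will be summarized descriptively". Describing subjects still under observation is a legitimate target in an uncontrolled safety extension. Attrition is visible too: by-visit HAMD-17 summaries report the number of subjects, and discontinuations are tabulated by reason. All of this stands and lowers the importance of the point. But a count of leavers does not show what the rate would be with treatment failures retained.

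A reader might also infer more than the documents support:

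- **That the rates must rise.** Lack of efficacy is one of 11 reasons listed in Protocol 4.4, and no count is given. The sponsor stop adds loss that is plausibly unrelated to outcome, and adverse-event leavers may be in remission.
- **That Week 28 to 52 rates describe only survivors.** Early-termination scores count in their own window, some windows are wide (OL Week 28 is days 155 to 238), and Protocol 4.4.1 asks sites to try to complete the early-termination visit. The loss starts in the following window.
- **That no other table exists.** Table specifications are in a separate document (SAP 1). What can be said is that the SAP specifies none.

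**Conclusion.** The point holds as a risk to interpretation. As written, the SAP can show a rise in response or remission that is only attrition, and it specifies no analysis that would separate the two. Direction and size depend on the response rate among leavers, which the documents do not give. Under the assumed 40% true rate and 30% loss, the observed rate runs from 31.4% to 57.1% as responders among leavers go from 60% to 0%, with 47.1% for the mixed case. The upper figure requires every leaver to be a non-responder and should not be read as the expected size. No test, error rate or sample-size argument is affected.

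**What to change.** Keep the observed-case table and print n beside each rate. Add one supportive table of response and remission to SAP 13, defined as follows:

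1. **Denominator at each visit:** all Safety Analysis Set subjects whose planned visit date falls before the study stop date, applied alike to every subject whatever the exit reason. The documents do not give that date, so the SAP should name it.
2. **Failures:** subjects who discontinued before the visit for lack of efficacy or an adverse event count as non-responders and non-remitters.
3. **All other exits** (death, lost to follow-up, withdrawn consent, physician decision, non-compliance, protocol deviation, prohibited medication, pregnancy, other): state one rule, for example non-responder in this table, and show their number.
4. **Subjects still in the study without a usable total at the visit:** state a rule for these too, since they are in the denominator.

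The cost is one table from data already collected. The table depends on the recorded discontinuation reason and is conservative for adverse-event leavers who were in remission when they left. It should therefore sit beside the planned table and not replace it.
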